At the enrollment visit in the private exam room, the study nurse will describe the details of the study verbally and women will be provided an opportunity to ask any questions. The participant eligibility will be verified using the eligibility form. Those who qualify and are able and willing will then undergo the consenting process, in which the two copies of the consent form, one for the study documentation and one for the participant to take home for her records. The consent form includes study information such as contact information for study doctors in case of questions, concerns, or emergencies. The study nurse and the participant will go through a consent form, which will be read by the study nurse to those participants who are illiterate, allowing for sufficient time for questions and answers about the procedures and processes.

All participants must sign and date the most current IRB-approved version of the study specific informed consent prior to participating in the study or having any study specific procedures. It will be the responsibility of [name] and coordinator/study manager to ensure that participants are consented with the latest approved version of the informed consent. The study staff will ensure that all sections of the informed consent that require completion by participants are completed.

If a participant does not sign an informed consent prior to a study specific procedure, the participant will not be considered eligible and will not be screened or registered. A copy of the informed consent will be archived in the participant's research file. The informed consent process will be documented in the study log.

X.B.2. Protections Against Risk

Protection against the risk of inadvertent disclosure of confidential information is addressed by the standard procedures at the Rwandan study site, including: (i) storing completed paper copies of study forms and other hard copy information (described above), identified by study number

only, in a filing system separate from the name-address file of participants in the study; and (ii) only the designated local personnel have access to cross-reference the files.

Copies of signed consents will be stored in locked file cabinets in a locked room, with access restricted to study personnel only, at the study lab. Data will be entered or transferred to a secure REDCap database, with access to personal information restricted to the local staff.

Study data will be stored in REDCap and maintained on password protected study computers behind the institution firewall. REDCap is a secure, web-based application designed to support data capture for research studies providing: 1), an intuitive interface for validated data entry; 2) audit trails for tracking data manipulation and export procedures; 3) automated export procedures for seamless data downloads to common statistical packages; and 4) procedures for importing data from external sources. REDCap is hosted on a secure server and has undergone a Governance Risk & Compliance Assessment by All REDCap electronic data files shared with Albert Einstein College of Medicine will be maintained by the HIPAA-compliant Epidemiology Study Management and Informatics Core Facility (ESMI) at Einstein. The Albert Einstein College of Medicine policy on use of REDCap can be found at:
http://ric.einstein.yu.edu/ric_files/REDCap%20Appropriate%20Use%20Policy.pdf

Side effects/adverse events due to ablative treatments are generally minor (pain, cramping, and watery discharge). Any pain, bleeding, or stress that might occur related to colposcopy, biopsies, vaginal collections, and/or LEEP are typically modest and no greater than those risk for the primarily HIV[-] women in the general population for whom cervical screening is recommended by the WHO and most countries in the world. These side effects and serious adverse events will be managed through referral to the Gynecology department at RMH. As needed, consults with other medical specialists will be sought. Care for study-related adverse events will be paid for by the study. Serious adverse events will be reported to the IRBs.

Study nurses have been trained in pre- and post-counseling for HIV testing and will provide support to participants taking rapid HIV tests. They will be trained to assist participants with any anxiety or discomfort experienced through responses to questionnaires and/or testing HPV positive.

Although women who are pregnant are at very low risk of adverse events due to the enrollment and follow-up procedures in this study, it is important to avoid any potential perceived risk. For this reason, all participants will have a pregnancy test performed at all visits. If they are found to be pregnant, they will be exited from the study and invited to enroll when they are at least 6 weeks post-partum.

Risks associated with blood collections will be minimized by having a trained and experienced health worker draw blood.

Because of the nature of the study, we believe that there is a very low risk of incidental findings related to participants' health and well-being. That said, we will have language in the informed consent acknowledging the possibility of incidental findings, and whether and how that information will be disclosed confidentially to the individual. Should there be an incidental health finding, the information will be provided to the participant if they consented to do so, and the research team will ensure that basic educational information about the nature of the finding is made available and will assist in finding the appropriate referral to a clinician or specialist for care if so desired.

X.C. Potential Benefits of the Proposed Research to Research Participants and Others

Participants who have not previously tested positive for HIV will be provided an opportunity for rapid HIV testing with pre- and post-counseling. Any participant who tests positive for the rapid HIV test at enrollment will be connected to the local HIV clinic for evaluation and management. Because this study is recruiting young women, it is very unlikely that they will have precancer. But by participating in this study, their precancer will be diagnosed and treated. This study will generate important information contributing to the knowledge of HPV vaccine effectiveness and immunity in Rwanda women living with HIV and without HIV. The findings will help to inform the development of programs and interventions for communities.

XI. LIMITATION AND FUTURE DIRECTIONS

Several limitations in the proposed study are worth noting. Our study is not a randomized trial, but the study populations will be selected from different cohorts of women: WLWH who are too old to have been vaccinated, WLWH and HIV[-] women who were vaccinated with 3 doses, WLWH and HIV[-] women who were vaccinated with 2 doses, and HIV[-] women who were too old to have been vaccinated. We have proposed several approaches to account/adjust for those age differences but as with any observational study, these techniques are unable to completely control for this bias.

We are using 6-12 month persistence as a proxy for cancer risk but ideally, we want to measure the impact of Gardasil® on high-grade cervical and anal abnormalities as a more proximal surrogate for cancer risk. The population will be still too young to have large numbers of these endpoints although we will look at these endpoints in secondary analyses. The longer-term effectiveness of Gardasil® through years of peak HPV exposure cannot be assessed in the 5-year time period of a single grant.

Our hope is to conduct follow-up studies of this newly established cohort of WLWH to assess the durability of immunogenicity and protection, including protection against high-grade cervical and anal abnormalities, offered by HPV4 for WLWH, as well as continuing to study the natural history of HPV in WLWH living in SSA. Eventually, as noted above (**Section VIII.**), we will be

[figure not shown]
well-positioned to examine the impact of HPV vaccination on cancer incidence in WLWH by linkage of electronic databases that we have helped/will help create.

XII. DISSEMINATION OF RESEARCH RESULTS

[figure not shown]
We plan to publish a series of 10 or more scientific reports in peer-review scientific journals. As building research capacity in Rwanda is a major goal of this U54 grant, all members of the research team will be asked and supported to lead at least one analysis and one manuscript preparation, based on interests and expertise. A publication grid is in development to assign analytic and publication responsibilities equally and collaboratively among both Rwandan and U.S. investigators.

XIII. TIMELINE

Pending approvals and situations in the field with the COVID-19 pandemic, we anticipate starting enrollment in September 2021. Enrollment will take approximately 14-16 months with completion of follow-up visits 6-12 months after that. All colposcopy and treatment visits should be completed by mid-2023.

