HPV31/33/35/39/45/51/52/53/56/58/59/66/68 for exploratory aims. Participants positive for high-risk HPV and/or HPV6/11 on any sample will have a 6-12 month follow-up visit to measure HPV type-specific persistence - a surrogate endpoint recommended by the WHO (87). At young ages, the risk of precancer is very low, but for safety purposes, participants will be offered colposcopy if they have a persistent high-risk HPV cervical infection and anoscopy if they have a persistent HPV16/18 anal infection. Main outcomes will be prevalence and 6-12 month type-specific persistence of cervicovaginal (as an excellent proxy for cervical sampling (87)), anal, and/or oral infections by HPV6/11/16/18 as well as antibody titers for HPV6/11/16/18. Cervical and anal biopsy specimens diagnosed as CIN2+ or AIN2+, respectively, will also be tested for the 15 high-risk and 2 low-risk HPV types for secondary outcomes. In an exploratory aim, we will examine risk factors, including the cervicovaginal microbiome (88), for HPV type-specific persistence in WLWH and HIV[-] women.

At enrollment, blood will be collected for plasma from all participants. In the study laboratory, a stratified random sample of specimens will be selected to measure by ELISA anti-HPV16 and -HPV18 antibody titers and compare HPV-vaccinated WLWH. We will test titers in at least 1,302 samples ($n \geq 548$, 50% with three doses and 50% with two doses of Gardasil®, for both HPV-vaccinated WLWH and for HPV-vaccinated HIV[-] women; $n \geq 108$ for both HPV-vaccinated WLWH and for HPV-vaccinated HIV[-] women as controls) and up to 3,028 samples.

VI.B. Study Locations

In Kigali, the study staff will work with five public clinics that participate in the International Epidemiology Databases to Evaluate AIDS (IeDEA) program and the WE-ACTx private clinic (**Table 2**). Study investigators and staff successfully worked with these clinics in a cervical cancer screening study of 5,000 WLWH (83). If needed, the staff will work with up to four other public health clinics to recruit additional participants.

Table 2. Study enrollment sites	
IeDEA Sites	Non-IeDEA sites
1. Busanza health center (HC)	1. Cor-unum HC

2. Gikondo HC 3. Kicukiro HC 4. Nyarugunga HC 5. Rwanda Military Hospital 6. WE-ACTx private clinic	2. Kacyiru HC 3. Remera HC 4. Rwampara HC
---	---

VI.C. Target Population

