This study will recruit women attending collaborating clinics and women from the communities surrounding those clinics. Three groups will be recruited:

- 757 HPV-vaccinated WLWH (Group 1),
- 757 HPV-unvaccinated WLWH (Group 2), and
- 757 HIV[-] women who are HPV-vaccinated (Group 3)
- 757 HIV[-] women who are HPV-unvaccinated (Group 4)

Within the HPV-vaccinated groups 1 and 3, the study will recruit at least 274 women with three doses and 274 women with two doses, with the remaining 209 will not be selected by the number of doses and may have 2 or 3 doses. The number of doses of HPV vaccination a woman received is dictated by introduction of HPV vaccination in Rwanda as previously shown in **Table 1**. In general, most Rwandan women born in 2003 or later will have been vaccinated with two doses of Gardasil®, women born between 1996 and 2002 will have been vaccinated with three doses of Gardasil®, and women born in 1995 or earlier will be unvaccinated.

Table 3. Target population by HIV status and age

HIV Status	Approximate number of HPV vaccine doses	Birth year	Age at year of study enrollment (years)		N
			in 2021	in 2023	
WLWH	3 doses	1996-2002	19-25	21-26	274
	2 doses	2003-2005	16-18*	18-20	274
	2 or 3 doses	1996-2005	19-25	18-26	209
	0 doses - unvaccinated	1993-1995	26-30*	28-31*	757
HIV[-]	3 doses	1996-2002	19-25	21-26	274
	2 doses	2003-2005	16-18*	18-20	274
	2 or 3 doses	1996-2005	19-25	18-26	209
	0 doses- unvaccinated	1993-1995	26-30*	28-31*	757
TOTAL					3,028

*Only women age 18-28 are eligible for enrollment.

Therefore, we will recruit by age, which will serve as a useful and very good proxy for HPV vaccination status, which otherwise would be difficult to confirm in real time at enrollment. HPV vaccination status then will be confirmed by retrospective review of the HPV vaccination records kept by the Rwanda Ministry of Health (MoH), who are collaborating on this project. The number of women recruited will therefore be stratified by age (as proxy for vaccine status) and HIV status (**Table 3**).

VI.D. Eligibility Criteria

VI.D.1 Inclusion Criteria

1. Gender: Female
2. Age: 18-28 years. The age of inclusion criteria will likely be restricted as age-specific enrollment goals are met.
3. Physically and mentally able and willing to participate in the study.
4. Willing to provide written and signed or thumb printed, informed consent.

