For Specific Aim 2 (**Section VII.B**) anti-HPV16 and HPV18 IgG antibody titers will be measured from plasma by an ELISA based on a previously described method (97, 98) and according to the protocol established by the FNLCR HPV Serology Laboratory (99). Only anti-HPV16 and HPV18 IgG antibody titers, and not titers for all 4 HPV types, will be evaluated as antibody titers are correlated between antibody responses for the different types. HPV16 and HPV18 are the two most important HPV types and cause approximately 70% of cervical cancers (19). HPV16 tends to induce the highest titers while HPV18 tends to induce the lowest titers among the 4 types (100, 101) and therefore measuring the two types gives us a range in responses while using study resources cost effectively. The FNLCR Serology Laboratory will teach the ELISA protocol to [name] (co-I; Einstein), who will oversee the transfer of this ELISA assay to the study lab in Rwanda.

First, 20% of each group will be run at the Frederick NCI lab, then the results will be replicated at the study lab (masked to the original results), and then the remaining 80% of the testing will be finished at the study lab. As an additional quality control measure, a 10% random sample of specimens will be re-run at the NCI Frederick lab (masked to the original results) (inter-laboratory reliability) and another 10% random sample of specimens at the study lab (intra-laboratory reliability). The study lab will achieve at least 90% correlation for both anti-HPV16 and -HPV18 titers with FNLCR Serology Laboratory on the first 20% of specimens tested before the study lab embarks on testing the last 80% of specimens (101). Positive (e.g., IS standards (102, 103)) and negative controls (e.g., negative plasma) will be included in some testing plates to monitor assay performance per WHO recommendations (104).

VI.I.3. CVM Analyses

Baseline and follow-up specimens collected for baseline HPV-positive participants will be tested for cervicovaginal microbiota by next-generation sequencing (NGS) for our Exploratory Aim (**Section VII.C.**) on short-term HPV persistence. The first 20% of specimens will be tested in both the collaborating lab and the study lab until acceptable agreement is achieved (see below) after which the remaining 80% of specimens will be tested at the study lab with retesting 10% for quality control.

VI.I.4. Pathology

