Sample size calculation relates to the relative effectiveness measure as discussed. Under above assumptions, a sample size of 757 vaccinated and 757 unvaccinated WLWH will provide $\geq 80\%$ power ($p=0.05$) to detect an OR of ≤ 0.5 for 6-12 month persistent HPV6/11/16/18 infections, relative to HPV35/39/51/52/53/56/58/59/66/68 (but not HPV31/33/45 because of possible cross protection), in Gardasil®-vaccinated vs. -unvaccinated WLWH. Consequently, because there will be more participants with a prevalent infection than 6-12 month persistent HPV infection (because there are no losses to follow-up or HPV viral clearance for which to account), there will

be $\geq 80\%$ power ($p=0.05$) to detect a OR of ≤ 0.75 in point prevalence of HPV6/11/16/18 infection relative to HPV35/39/51/52/53/56/58/59/66/68, in Gardasil®-vaccinated vs. - unvaccinated WLWH.

VII.B. Specific Aim 2

To quantify, and examine the determinants of, long-term antibody responses to, HPV vaccination.

VII.B.1. Analyses.

Geometric mean titers (GMT) and seropositivity (seroconversion) will be compared between 1) HPV-vaccinated WLWH and HPV-vaccinated HIV[-] women, overall and stratified on the number of vaccine doses, 2) HPV-vaccinated and unvaccinated WLWH, overall and by the number of doses received by the HPV-vaccinated WLWH, and 3) three vs. two doses for HPV-vaccinated WLWH and 4) HPV-vaccinated and unvaccinated HIV[-] women, overall and by the number of doses received by the HPV-vaccinated HIV[-] women.

Differences in GMT and seropositivity will be tested for statistical significance using the Mann-Whitney and Fisher's exact tests, respectively. ANOVA and logistic regression models will be used to adjust for/assess the association of other factors (e.g., age at vaccination, age at enrollment into the study, number of doses, HIV status [positive vs. negative and current antiretroviral therapy, CD4 counts, and HIV viral load] and history [e.g., CD4 nadir], and detection of HPV genotypes, etc.) with GMT and seropositivity, respectively.

Among vaccinated and unvaccinated HPV seropositive WLWH, the association between HPV antibody titer and presumed route of HIV acquisition (either maternal to child or behavioral) will be examined.

VII.B.2 Sample Size/Power to compare Gardasil®-vaccinated WLWH vs. Gardasil®-vaccinated HIV[-] women.

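### The minimum serology sample in VI.A labels its control strata HPV-vaccinated, so no unvaccinated titers are guaranteed for two planned Aim 2 comparisons, and its total (1,302) does not match its parts (1,312)

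*Combined protocol and SAP*

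**What the plan says.** Section VI.A describes a stratified random sample of plasma for the anti-HPV16 and anti-HPV18 ELISA. The commitment is: "We will test titers in at least 1,302 samples". It is made up of at least 548 vaccinated WLWH and at least 548 vaccinated HIV-negative women, each split equally between two and three doses, and then at least 108 "for both HPV-vaccinated WLWH and for HPV-vaccinated HIV[-] women as controls". Testing may extend to all 3,028 participants.

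Section VI.C supports the 548. Within each vaccinated group, "the study will recruit at least 274 women with three doses and 274 women with two doses". It also defines the unvaccinated groups that could serve as controls: Group 2 (unvaccinated WLWH) and "757 HIV[-] women who are HPV-unvaccinated (Group 4").

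Section VII.B.1 lists four comparisons of geometric mean titer and seropositivity. Item 2 is "HPV-vaccinated and unvaccinated WLWH, overall and by the number of doses received by the HPV-vaccinated WLWH". Item 4 is "HPV-vaccinated and unvaccinated HIV[-] women, overall and by the number of doses received by the HPV-vaccinated HIV[-] women". A further analysis reads: "Among vaccinated and unvaccinated HPV seropositive WLWH, the association between HPV antibody titer and presumed route of HIV acquisition".

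Section VI.I.2 says of the assay transfer: "First, 20% of each group will be run at the Frederick NCI lab". It does not name the groups or give their sizes.

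**The concern.** The control strata in VI.A carry the same label as the main strata, so the controls are drawn from the populations they are meant to be compared with. Items 2 and 4 of VII.B.1 need titers from Groups 2 and 4, and the written minimum supplies none. The route-of-acquisition analysis would lose its unvaccinated part.

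This matters because the sentence is the only place in the text available that gives a number for control plasma, and it governs a sample drawn in the laboratory. Someone following it literally would meet every stated floor and still leave two of the four Aim 2 group comparisons without a comparator.

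The total is a second, smaller fault in the same sentence. The stated minimum is not the sum of its strata, and no basis for 108 is given, so the reader cannot tell which number to trust.

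**Working it through.** **Inputs.** From VI.A: stated minimum 1,302; main strata at least 548 each (two groups); control strata at least 108 each (two groups); ceiling 3,028. From VI.C: 274 three-dose and 274 two-dose women in each vaccinated group; 757 women per group. From VII.B.2: sample sizes of 274 and 548.

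**1. The stated total.**
- Main strata: 2 × 548 = 1,096.
- Control strata: 2 × 108 = 216.
- Sum: 1,096 + 216 = 1,312, against 1,302 stated. The gap is 10 (10 / 1,302 = 0.77%).
- Counting only one control stratum gives 1,096 + 108 = 1,204, so that reading does not recover 1,302 either.

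**2. Which number is wrong.**
- If the total is right and 108 is right, the main strata would be (1,302 − 216) / 2 = 543. That is excluded: 274 + 274 = 548, and 548 also appears in the Executive Summary and VII.B.2.
- If the total is right and 548 is right, the control strata would be (1,302 − 1,096) / 2 = 103.
- So either the control floor should be 103 or the total should be 1,312. The text does not say which.

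**3. Unvaccinated titers guaranteed.**

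| Stratum as written in VI.A | Minimum n | Unvaccinated |
|---|---|---|
| Vaccinated WLWH | 548 | 0 |
| Vaccinated HIV-negative | 548 | 0 |
| Vaccinated WLWH, controls | 108 | 0 |
| Vaccinated HIV-negative, controls | 108 | 0 |

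The guaranteed number for Groups 2 and 4 is 0. The 216 control assays, 216 / 1,312 = 16.5% of the minimum, fall on vaccinated women.

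**4. Would a feasibility check expose the label?** Under the literal reading each vaccinated group supplies 548 + 108 = 656 women, which is below 757. The draw can be carried out, so the counts alone would not reveal the error.

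**5. Do other sections supply an unvaccinated number?**
- The Executive Summary and VII.B.2 give serology numbers for vaccinated women only.
- VI.C gives dose targets within the vaccinated groups, and enrolment numbers but no assay numbers for the unvaccinated groups.
- VI.F.1.b has blood drawn from all participants, which makes samples available but does not commit them to testing.
- VI.I.2 refers to each group without a number.

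The Appendix I diagram was not shown in the copy reviewed.

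**6. Does 103 versus 108 matter for precision?** VII.B.2 states a detectable difference of 30% with 274 per group. Reading this as a ratio of 0.70, with 80% power and two-sided 0.05, the implied SD of log titer is |ln 0.70| / (2.80 × √(2/274)) = 1.49. With 548 per group this gives 1 − exp(−1.49 × 2.80 × √(2/548)) = 22%, which reproduces the plan's figure. Using the same SD for 548 vaccinated against unvaccinated controls, the detectable reduction is 35.6% with 108 controls and 36.1% with 103. The equal SD for unvaccinated women is an assumption. On that basis the 10-sample discrepancy has almost no statistical effect, and the label is the part that matters.

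**The case against.** The strongest reply is that the intent is plain. Women cannot sensibly be controls for their own group, and VII.B.1 names unvaccinated comparators in both HIV strata. The ceiling of 3,028 exceeds the 2 × 757 = 1,514 women in the vaccinated groups, so testing of Groups 2 and 4 is contemplated. X.A.2 says every participant gives blood for titer testing. Because VI.C numbers four groups, the reference to each group in VI.I.2 most naturally includes the unvaccinated ones. Residual plasma is stored, so even a wrong draw could be repaired later.

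Two further points concern size. The 216, the 16.5% and the 656 assume that the two floors for each vaccinated group are additive; read strictly, the first floor could already satisfy the second. And a minimum of 1,302 is not breached by testing 1,312.

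Most of this stands as a limit on consequences. A careful reader would probably supply the missing prefix, and no assays are lost through the wrong total. It does not repair the rule, because none of these sections commits to a number of unvaccinated samples. On additivity, overlapping floors would give a minimum of 1,096, further from 1,302 than the additive sum, so the stated total supports separate strata. A one-digit conversion error in the copy reviewed cannot be excluded for the total, and the sponsor can settle that by looking at the source file.

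**Conclusion.** The concern holds. As written, VI.A guarantees no unvaccinated titers. Items 2 and 4 of VII.B.1 therefore have no guaranteed comparator, and the route-of-acquisition analysis would be incomplete. The stated total is 10 below the sum of its parts.

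This is a defect in a written sampling rule, most likely a dropped prefix. It is not a forecast that the titers will be missing. The vaccinated WLWH versus vaccinated HIV-negative comparison, the dose comparison and the power figures in VII.B.2 do not depend on it. The conclusion on the label rests only on the text; the 216 and 16.5% also rest on treating the control strata as separate from the main strata. It should be corrected, but it does not threaten the study's powered comparisons.

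**What to change.** In VI.A, confirm and relabel the control strata as HPV-unvaccinated WLWH (Group 2) and HPV-unvaccinated HIV-negative women (Group 4), with a stated minimum for each. Confirm the control number and make the total agree: 1,312 if 108 stands, or 1,302 if 103 was meant. A sentence giving the basis for the control number would help, since none is provided.

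As a separate point of wording, the same edit could align the antibody outcome in VI.A, which names four HPV types, with VI.I.2, which limits the assay to HPV16 and HPV18.

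The cost is a text correction. Blood is already drawn from every participant, and no assays are needed beyond the floors already stated.
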